#### **4.5.3.2. Vital Signs**

Pre-dose systolic blood pressure, diastolic blood pressure, pulse rate and body temperature including change from baseline at all visits will be summarised.

#### **4.5.3.3. ECG**

[figure not shown]
Change from baseline (for post-baseline timepoints) values for QTc(F), and heart rate will be summarised by treatment for Baseline, Week 2, Week 26, Week 28, and Week 52. ECG findings will be summarised by visits.

Individual maximum QTc(F) values will also be summarised to show the number of subjects with maximum values (msec) post-baseline relative to baseline in the following categories: Decrease, no change or increase to  $\leq 450$ , increase to  $450 < \text{to } \leq 480$ , increase to  $480 < \text{to } \leq 500$ , increase to  $500 < \text{to } \leq 530$  and increase to  $> 530$ . QT uncorrected values will be summarised to show the number of subjects with maximum values (msec) post-baseline relative to baseline in the following categories: Decrease, no change or increase to  $< 600$  and increase to  $\geq 600$ .

Additionally, individual maximum changes from baseline in QTc(F) values will be summarised to show the number of subjects with maximum changes (msec) in the categories: increase of  $\leq 30$ , increase of 31 to 60 and increase of  $> 60$ .

All ECG values for participants with protocol defined QT stopping criteria will be listed.

CCI

A large black rectangular redaction box covers the majority of the page below the CCI label, starting just below the text and ending above the section header 4.5.4.

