Study visits may be conducted remotely or virtually, however, in-person clinic visits are required for those visits with study drug administration, 12-lead ECG or spirometry assessments, as detailed in the Schedule of activities (SoA): Visit 1, Visit 2, Visit 6, Visit 7, Exit Visit 12 and Withdraw from Study (WS) Visit (if applicable). For WOCBP the follow up visit should be conducted as onsite visit or home visit (where applicable). Follow-up phone call is only applicable for male and WONCBP.

Data Monitoring/ Other Committee: Yes

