1.3. Schedule of Activities (SoA)

| Protocol Activity | Intervention Period and Exit Visit (visit window is ± 7 days) | | | | | | | | | | | | Follow-up visit/call or Withdrawal Visit (± 7 days) | Notes | |
|--|---|----|----|----|-----|-----|-----|-----|----------------|-----|----------------|----------------|--|-----------------------|--|
| | V1 * | V2 | V3 | V4 | V5 | V6 | V7 | V8 | V9 | V10 | V11 | Exit Visit V12 | FU ⁱ | WS Visit ^b | |
| Visit | V1 * | V2 | V3 | V4 | V5 | V6 | V7 | V8 | V9 | V10 | V11 | Exit Visit V12 | FU ⁱ | WS Visit ^b | FU=Follow-up visit WS=Withdrawn from study visit |
| Study Week | 0 | 4 | 8 | 12 | 20 | 26 | 28 | 32 | 36 | 40 | 48 | 52 | 56 | | |
| Study Day | 1 | 28 | 56 | 84 | 140 | 182 | 196 | 224 | 252 | 280 | 336 | 364 | 392 | | |
| General Eligibility Assessments | | | | | | | | | | | | | | | |
| Informed Consent ^a | X | | | | | | | | | | | | | | See footnote a. |
| Inclusion/Exclusion Criteria | X | | | | | | | | | | | | | | |
| Demography data collection | X | | | | | | | | | | | | | | |
| Medical history | X | | | | | | | | | | | | | | Changes including cardiovascular (CV), CV risk factors, asthma including exacerbations, vasculitis, allergies and anaphylaxis |
| Smoking Status | X | | | | | | | | | | | | | | |
| Parasitic screening | X | | | | | | | | | | | | | | Parasitic screening should have been performed prior to treatment in the OLE only if the participant has travelled to high risk countries in the past six months. For details refer to study reference manual (SRM). |
| Safety assessments | | | | | | | | | | | | | | | |
| Concomitant Medication Assessment ^c | X | X | X | X | X | X | X | X | X ^h | X | X ^h | X | | X | See footnote c. |
| Physical Examination | (X) | | | | | | | | | | | X | | X | |

CONFIDENTIAL

212895

Protocol Amendment 2

| Protocol Activity | | Intervention Period and Exit Visit (visit window is ± 7 days) | | | | | | | | | | | | Follow-up visit/call or Withdrawal Visit (± 7 days) | Notes | |
|---|----------------|---|----|----|-----|-----|-----|-----|----------------|-----|----------------|----------------|----------------|--|-----------------------|--|
| | | V1 * | V2 | V3 | V4 | V5 | V6 | V7 | V8 | V9 | V10 | V11 | Exit Visit V12 | FU ⁱ | WS Visit ^b | |
| Visit | V1 * | | | | | | | | | | | | | | | FU=Follow-up visit WS=Withdrawn from study visit |
| Study Week | 0 | 4 | 8 | 12 | 20 | 26 | 28 | 32 | 36 | 40 | 48 | 52 | 56 | | | |

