| Study Day | 1 | 28 | 56 | 84 | 140 | 182 | 196 | 224 | 252 | 280 | 336 | 364 | 392 | | | |
| Vital Signs | X ^d | | X | | X | X | X | | | X | | X ^d | | X ^d | | See footnote d. |
| 12-lead ECG | (X) | X | | | | X | X | | | | | | X | | X | ECG must be performed and assessed pre-dose. Twelve-lead ECG central overread values should be used at all visits with the exception of Visit 1 and Visit 6 where 12-lead ECG machine read values should be used. |
| Adverse Events/Serious Adverse Event Assessment | X ^e | X | X | X | X | X | X | X | X ^h | X | X ^h | X | X | X | | See footnote e. |
| Laboratory Assessments | | | | | | | | | | | | | | | | See footnote f. All WOCBP as determined in prior study (206713/ 213744) must continue their highly effective contraceptive method without any interruptions between prior study and enrolment in this study. See Section 5.1 and Section 8.2.5 for additional details |
| Urine Pregnancy Test ^f (WOCBP only) | X | X | X | X | X | X | X | X | X ^h | X | X ^h | X | X | X | | |

CONFIDENTIAL

212895

Protocol Amendment 2

| Protocol Activity | | Intervention Period and Exit Visit (visit window is ± 7 days) | | | | | | | | | | | | Follow-up visit/call or Withdrawal Visit (± 7 days) | Notes | |
|-------------------------|------|---|----|----|-----|-----|-----|-----|----------------|-----|----------------|-----|----------------|--|-----------------------|--|
| | | V1 * | V2 | V3 | V4 | V5 | V6 | V7 | V8 | V9 | V10 | V11 | Exit Visit V12 | FU ^a | WS Visit ^b | |
| Visit | V1 * | | | | | | | | | | | | | | | FU=Follow-up visit WS=Withdrawn from study visit |
| Study Week | 0 | 4 | 8 | 12 | 20 | 26 | 28 | 32 | 36 | 40 | 48 | 52 | 56 | | | |
| Study Day | 1 | 28 | 56 | 84 | 140 | 182 | 196 | 224 | 252 | 280 | 336 | 364 | 392 | | | |
| Urinalysis | (X) | | | | | | X | | | | | | | X | | Note: Urinalysis to be performed using dipstick test. If results are abnormal a second urine sample should be taken and sent to central laboratory. China Only: For China sites the urine specimen may be sent to the central laboratory for routine urinalysis instead of performing a local urine dipstick. |
| Clinical Chemistry | (X) | X | X | X | X | X | X | | | X | | X | | X | | Include liver chemistry. |
| Immunogenicity sample | (X) | | | X | | X | | | | X | | X | | X | | |
| CC1 | | | | | | | | | | | | | | | | CC1 |
| Efficacy Assessments | | | | | | | | | | | | | | | | |

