6.7. Treatment of Overdose

The dose of GSK3511294 that is considered to be an overdose has not been defined. There are no known antidotes and there is no specific treatment for a suspected overdose. In FTIH study 205722 [GSK Document Number [RPS-CLIN-044550](#) or later], single SC doses of GSK3511294 up to 300 mg were well tolerated by adult participants with mild/moderate asthma (6 participants received a 300 mg SC dose).

Each PFS will enable the delivery of a single dose of study intervention (see Section [6.1](#)).

In the event of an overdose, the investigator should:

- Contact the Medical Monitor immediately.
- Treat the patient with active supportive care as dictated by the participant's clinical status in the knowledge of the long half-life (approximately 41 days) of GSK3511294.
- Closely monitor the participant for AE/SAE and laboratory abnormalities for 30 weeks following the last administered dose.
- Document the quantity of the excess dose as well as the duration of the overdosing in the CRF.

Decisions regarding discontinuation or delay of another dose of study intervention will be made by the investigator in consultation with the Medical Monitor based on the clinical evaluation of the participant.

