### 1.1. Objectives, Estimands and Endpoints

#### 1.1.1. Objectives and Endpoints

Objectives	Endpoints
Primary (Safety)	

 
To describe the long-term safety profile of GSK3511294 100 mg (SC) every 26 weeks in participants with severe asthma with an eosinophilic phenotype on top of existing asthma therapy over a 12 month open label extension phase
 
	
 
Incidence of AEs/SAEs over 52 weeks
 
Incidence of immunogenicity as measured by the presence of ADA/NAb to GSK3511294 over 52 weeks
 

Secondary (Efficacy)	

 
To evaluate the effects of long-term dosing of GSK3511294 100 mg (SC) every 26 weeks on a range of clinical markers of asthma control and additional efficacy assessments on top of existing asthma therapy over a 12 month open label extension phase
 
	
 
Annualized rate of clinically significant exacerbationsa over 52 weeks
 
Change from Baseline in Asthma Control Questionnaire-5 (ACQ-5) score at discrete timepoints during the 52 week period
 
Change from Baseline in St. George's Respiratory Questionnaire (SGRQ) total score at Week 26 and Week 52.
 
Change from Baseline in pre-bronchodilator FEV1 at Week 26 and Week 52
 

Other	

 
To describe the long-term safety profile of GSK3511294 100 mg (SC) every 26 weeks in participants with severe asthma with an eosinophilic phenotype on top of existing asthma therapy over a 12 month open label extension phase
 
	
 
ECG assessments at discrete timepoints during the 52 week period 
 
Change from baseline in ECG values
 
Maximum QTc values post baseline
 
Maximum increase in QTc values post baseline
 
ECG findings
 
 
 
Change from baseline in vital signs including blood pressure (BP), body temperature, and pulse rate at discrete timepoints during the 52 week period
 

Objectives	Endpoints
	
 
Change from baseline in laboratory parameters (including haematological, clinical chemistry) and hepatobiliary laboratory abnormalities, at discrete timepoints during the 52 week period
 

Pharmacodynamic (PD) <small>CCI</small>	

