## 1.2. Study Design

Overview of Study Design and Key Features													
Week	0'	4'	8'	12'	20'	26'	28	32'	36'	40	48	52	56'
Visit	1'	2	3'	4'	5'	6'	7'	8	9'	10'	11	12'	13'

The diagram illustrates the study timeline. It starts with 'Visit 1' (Exit-Visit for Study 206713/213744) at Week 0. This is followed by the 'Study Intervention Period' (Visit 1 dose at Week 0, Visit 2 dose at Week 26). The intervention period ends with 'Visit 13' (Follow-up Visit) at Week 56. A '4-Weeks' follow-up period follows Visit 13. Arrows indicate the timing of doses and visits relative to the start of the intervention period.
													

*The Exit-Visit in 206713/213744 will serve as the Baseline Visit (Visit 1) for this study (212895).  **Participants will remain on standard-of-care asthma therapy, which may be adjusted during the study at the discretion of their physician.
													
Design Features	
 
multicentre, single-arm, open-label 12-month extension study
 
52-week treatment period
 
Participants who completed either study 206713 or 213744 will have the opportunity to participate in this study, regardless of which treatment they were previously randomized.
 
The total number of participants enrolled in this trial will not be greater than the combined number randomised into Studies 206713 and 213744.
 
Participants meeting all the inclusion criteria and none of the exclusion criteria will receive their first open-label dose of GSK3511294 SC at Visit 1 (baseline visit). Participants will receive a second open-label dose of GSK3511294 SC at 26 weeks after Visit 1, providing up to 52 weeks of treatment.
 
												
Study intervention	GSK3511294 100 mg SC												
Study intervention Assignment	All Participants will receive open label GSK3511294 100 mg SC												

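### The SAP's QTcF and heart-rate summary names a Week 2 timepoint that does not exist and leaves out the scheduled Week 4 ECG

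*SAP*

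**What the plan says.** SAP section 4.5.3.3 ties the change-from-baseline summary to named weeks: QTcF and "heart rate will be summarised by treatment for Baseline, Week 2, Week 26, Week 28, and Week 52". The same section adds, without naming weeks, that "ECG findings will be summarised by visits". It also asks for categories of maximum post-baseline QTcF and uncorrected QT, categories of maximum QTcF increase, and a listing for participants who meet the QT stopping criteria.

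The endpoint behind the summary is in SAP section 1.1.1: "ECG assessments at discrete timepoints during the 52 week period", with change from baseline in ECG values as its first component. SAP section 4.5.2.1 and protocol section 8.3.7 both list QTc prolongation as an adverse event of special interest.

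The protocol's Schedule of Activities (section 1.3) gives the weeks as "Study Week | 0 | 4 | 8 | 12 | 20 | 26 | 28" and onwards. The in-person visits required for dosing, ECG or spirometry are "Visit 1, Visit 2, Visit 6, Visit 7, Exit Visit 12", plus the withdrawal visit where it applies (protocol section 1.1, repeated in 4.1). The schedule's note on the ECG row says "ECG must be performed and assessed pre-dose", so the Week 26 tracing comes before the second dose.

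**The concern.** The by-timepoint table names a week at which nobody is seen and omits a week at which everyone is due an ECG. A programmer following the text would produce an empty Week 2 row and no Week 4 row.

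The missing row matters because of where it falls. Week 4 is the only scheduled ECG after the first open-label dose and before the pre-dose ECG at Week 26. For participants who had placebo in the parent study, it is the first scheduled ECG on depemokimab. Without it, the first mean QTcF change in the table comes from the end of the first dosing interval. The same text governs the interim report for regulatory submission, since SAP section 4.9.1 applies the plan's analyses at the interim cut.

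**Working it through.** **Inputs**

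- Weeks listed for the summary (SAP 4.5.3.3): Baseline, 2, 26, 28, 52.
- Visit weeks (protocol 1.3): 0, 4, 8, 12, 20, 26, 28, 32, 36, 40, 48, 52, 56. The visit table in SAP 1.2, under "Overview of Study Design and Key Features", also places Visit 2 at Week 4 and has no Week 2.
- ECG visits (ECG row in protocol 1.3, repeated in Table 4 of Appendix 9): Visits 1, 2, 6, 7 and 12, which are Weeks 0, 4, 26, 28 and 52, plus the withdrawal visit. Some cells in that row are displaced in the text available, but both copies mark Visit 2. The in-person visit list confirms it: Visit 2 has no dosing and no spirometry, so the ECG is what requires attendance.
- Visit window (protocol 1.3): ±7 days.
- Assessment windows (SAP 6.2.4): stated as not applicable.
- Half-life (protocol 6.7): "the long half-life (approximately 41 days) of GSK3511294".

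**Step 1: match the two lists**

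| | Post-baseline weeks |
|---|---|
| Listed in SAP 4.5.3.3 | 2, 26, 28, 52 |
| Scheduled ECGs, withdrawal visit excluded | 4, 26, 28, 52 |
| In both | 26, 28, 52 |
| Listed but not scheduled | 2 |
| Scheduled but not listed | 4 |

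One of four scheduled post-baseline timepoints (25%) is missing. It is also one of the two ECGs scheduled within four weeks after a dose: Week 4 after the first dose, and Week 28, two weeks after the second.

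**Step 2: could the Week 4 ECG count as Week 2?**

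Day 28 ± 7 gives Day 21 to Day 35. Week 2 is Day 14. The earliest in-window Visit 2 is 21 − 14 = 7 days too late, and the SAP has no rule that would reassign it. The Week 2 ECG mentioned in protocol section 2.3.1 belongs to the first-in-human study.

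**Step 3: what shifts in the table**

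The first populated post-baseline row moves from Day 28 to Day 182.

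For a rough sense of exposure, take the share of a single dose remaining as 2^(−days/41). This assumes single-exponential decline and ignores absorption and any earlier doses.

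| ECG | Days after latest dose | Share of that dose remaining | Over ±7 days |
|---|---|---|---|
| Week 4 | 28 | 2^(−28/41) = 0.62 | 0.70 (21 d) to 0.55 (35 d) |
| Week 26, pre-dose | 182 | 2^(−182/41) = 0.046 | 0.052 (175 d) to 0.041 (189 d) |
| Week 28 | 14 | 2^(−14/41) = 0.79 | not computed |

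**Step 4: a related label, with no effect**

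The ACQ-5 model in SAP 4.3.1.2 lists ten weeks: 4, 8, 12, 20, 24, 26, 28, 32, 40 and 52. ACQ-5 is scheduled at nine post-baseline weeks: 4, 8, 12, 20, 26, 28, 32, 40 and 52. Week 24 is not a visit. All nine scheduled weeks are listed, so nothing is lost and no estimate changes.

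**The case against.** The strongest reply is that this is a slip of the pen, not a choice of analysis. Four of the five listed timepoints match the schedule, so the authors evidently meant the scheduled ECG visits, and a programmer with no Week 2 visit in the data would probably tabulate Week 4. The output details sit in the Output and Programming Specification, which is not among the documents, so the shells may already be right. That reading of the cause is plausible. However, the SAP is the governing text, version 03 still carries the wrong week, and SAP section 4.10 declares no changes from the protocol's analyses. Using Week 4 without correcting the SAP would leave the report at odds with its plan.

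The second reply is that little is lost even on a literal reading. This largely stands. The categorical displays that would show individual prolongation use all post-baseline values, and SAP section 4.5.2.1 adds a separate display of QT-related events by MedDRA query. Stopping decisions follow protocol section 7.1.3, not this table, and the study tests no hypotheses.

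The third reply is that the half-life figures could mislead. On the same model the highest-exposure scheduled ECG is Week 28, at about 79%, and that row is kept. The documents also quantify no relation between concentration and QTc. Both points are fair. The figures show only that the Week 26 pre-dose ECG is a poor stand-in for Week 4 when describing the first dosing interval; they do not show that a QTc signal would be missed.

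**Conclusion.** The concern holds. SAP section 4.5.3.3 names one week with no visit and omits one of the four scheduled post-baseline ECG timepoints from the mean-change summary of QTcF and heart rate. Read literally, the first reported mean change is at Week 26 pre-dose instead of Week 4, when about 5% rather than about 62% of the first open-label dose remains under the simple decline model.

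The consequence is limited to one descriptive safety table, at the interim and final reports. No primary or secondary result is affected, and Week 4 ECGs still reach the other displays in the section. The mismatch itself rests only on the two documents' visit schedules and needs no assumption. Whether the programmed output would actually lack Week 4 is unknown without the output specification. A correction should be made because the table serves a named endpoint on an event of special interest and the change is nearly free.

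**What to change.** In SAP section 4.5.3.3, replace Week 2 with Week 4, so that the summary covers Baseline, Week 4, Week 26, Week 28 and Week 52. Check that the matching table shells in the output specification for the interim and final reports use the same list. In the same revision, delete Week 24 from the ACQ-5 visit list in SAP section 4.3.1.2 as a consistency correction with no effect on results.

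The cost is one changed word for the ECG summary, one deleted week for ACQ-5, and a check of the shells. No new data, visits or programming methods are needed.

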#### **4.5.4. Additional Safety Analyses**

The following additional safety analysis will be provided on Safety-Modified analysis set:

- Overview of all adverse events (including sites 250190, 250085 and 250523)
- Listing of all adverse events from sites 250190, 250085 and 250523

## 4.6. Immunogenicity Analysis

For the immunogenicity assessment, two types of anti-drug antibody (ADA) assays will be performed, a binding antibody assay and a neutralizing antibody assay (NAb).

[figure not shown]
For the binding assay, there will be a three-tiered analysis: screening, confirmation and titration. The screening assay produces a result of positive or negative relative to a screening cut point. Positive samples continue with the confirmation assay, which also produces a result of positive or negative relative to a confirmation cut point. For positive confirmation samples, a titre value will also be obtained to quantify the degree of binding in a titration assay, and the sample will be tested with the neutralizing assay, which also reports results as positive or negative. A sample that is positive in the confirmation assay is considered positive for anti-GSK3511294 antibodies.

The following descriptive summaries will be presented by visit using Safety population

- Summary of binding antibody assay results: it will summarise the binding antibody confirmatory assay results at each visit. Summary will include categories for negative and positive results, sub-categories for transient positive and persistent positive (see note below), and available titre values (min, median and max). It will also summarise the highest post-baseline binding antibody confirmatory assay result obtained.
- Summary of neutralizing antibody assay results: it will summarise the neutralising antibody assay results for participants with a positive binding antibody confirmatory assay result. Neutralising antibody assay results will be categorised as positive or negative. It will also summarise the highest post-baseline neutralizing antibody assay result obtained.
- Summary of AE by highest post-baseline binding antibody confirmatory assay result

Note: Visits will include baseline visit (V1) and all post-baseline visits where immunogenicity assessments were performed. The binding antibody confirmatory assay results are categorised as negative or positive. The positive results will have two subcategories: transient positive (defined as a single confirmatory positive immunogenic response that does not occur at the final study assessment) or persistent positive (defined as a confirmatory positive immunogenic response for at least 2 consecutive assessments or a single result at the final study assessment). For the summary of highest post-baseline binding antibody confirmatory assay result and neutralizing antibody assay result, subjects with both positive and negative results will be identified in the positive category. If a subject had titre results that fall into multiple titre result categories, they will be included in the highest category.

CCI

CCI

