| 
 Type III Hypersensitivity (Immune complex disease/vasculitis) | 
 Adverse effects of vascular inflammation consistent with immune complex disease were observed in 1 female monkey in the 1 month toxicity study after administration of 10 mg/kg. A further monkey had a minimal focal inflammation after administration of 100 mg/kg. Immune complex disease was not observed in the 6-month repeat dose (2 doses) study at the same doses. It is unknown if this will translate to humans as preclinical models are not necessarily predictive of clinical findings in humans. No AEs of Type III hypersensitivity have been reported with GSK3511294 in FTIH study 205722 in participants with mild to moderate asthma (36 participants received GSK3511294; 12 participants received placebo). | 
 Participants with current diagnosis of vasculitis will be excluded. Participants with high clinical suspicion of vasculitis at screening will be evaluated and excluded to from enrolment if diagnosed (Section 5.2). Daily monitoring of serious adverse events (SAEs) by medical monitor/SAE coordinator; regular systematic review of adverse event (AE)/SAE data from ongoing studies will be performed by a GSK safety review team. Protocol guidance on early identification of vasculitis events is provided (see Section 7.5). Participants with confirmed vasculitis or suspected vasculitis with no alternative explanation after the first open-label dose will not receive another dose of study intervention (see Section 7.1). |
| 
 Immunogenicity, anti-drug antibodies (ADAs) | 
 Biopharmaceutical products may elicit ADAs and neutralising antibodies (NAb), which have the potential to modulate PK or PD, or to produce adverse reactions. | 
 Blood samples will be collected for detection of both ADA and Nab (See Section 8.8). |

CONFIDENTIAL212895
Protocol Amendment 2

| Potential Risk of Clinical Significance | Summary of Data/Rationale for Risk | Mitigation Strategy |
|--|--|---|

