7.4. Reasons for Study Intervention Discontinuation and/or Study Withdrawal

The primary reason for a study intervention discontinuation and/or study withdrawal will be recorded in the eCRF. When a participant withdraws consent, the investigator must document the reason (if specified by the participant) in the eCRF.

7.5. Criteria for Follow-up of Potential Type III Hypersensitivity (Immune Complex Disease /Vasculitis)

Owing to the adverse findings of arterial inflammation that were observed in the 1-month, but not 6-month, nonclinical toxicology studies, events potentially representing type III hypersensitivity/immune complex disease/vasculitis should be promptly reported to GSK, and consultation with the medical monitor is encouraged. Treatment for the event will be given as medically required. If possible, ADA, C3, and C4 samples may be taken at the time of the event along with haematology, clinical chemistry and urinalysis.

Symptoms potentially suggestive of vasculitis include but are not limited to:

- persistent* fever (*where persistent is considered to be a duration of ≥ 2 days)
- persistent* muscle and joint pain
- persistent* rash
- persistent* fatigue
- symptoms of peripheral neuropathy, like numbness or weakness

- laboratory abnormalities, e.g., decreased platelets, elevated creatinine, decrease in complement C3/C4, abnormal urinary albumin/creatinine ratio

Participants who experience any of the above events should be monitored until the event resolves and/or a diagnosis is established.

The symptoms and clinical features are often non-specific and heterogeneous with respect to the time course over which they develop, organ involvement and the constellation of symptoms and severity. Early recognition of potential events of vasculitis is important to timely diagnosis and subsequent treatment.

The precise management will depend on the clinical evaluation at the time of presentation and ongoing assessment including consideration of relevant differential diagnoses. Given that there is often a differential for presenting symptoms such as infection, and indeed such factors may also precipitate immune related AEs, these factors (infectious, neoplastic, metabolic, toxic) should be given due consideration and ruled out.

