#### 6.2.4. Assessment Window

Not applicable for this study.

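### The AE-by-ADA table in SAP 4.6 uses ever-positive status with no rule on AE onset relative to the first positive sample, so it dilutes any real association and could reassure falsely.

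*SAP*

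**What the plan says.** SAP 4.6 lists three descriptive immunogenicity summaries. The third is the "Summary of AE by highest post-baseline binding antibody confirmatory assay result". The note that follows sets the rule for mixed results: "subjects with both positive and negative results will be identified in the positive category". A single transient positive is therefore enough. The note describes the samples used as follows: "Visits will include baseline visit (V1) and all post-baseline visits where immunogenicity assessments were performed". SAP 6.2.4, on assessment windows, reads "Not applicable for this study".

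The protocol's Schedule of Activities places immunogenicity samples at Visit 1 (or carried over from the parent study's Exit Visit), at Weeks 12, 26, 40 and 52, and at the withdrawal visit. Doses are given at Weeks 0 and 26.

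For suspected type III hypersensitivity, protocol 7.5 adds: "If possible, ADA, C3, and C4 samples may be taken at the time of the event". Protocol section 8 also allows unscheduled samples for safety reasons in general. The SAP does not say whether any of these enter the highest post-baseline result.

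Protocol 2.3.1 gives the reason for looking at ADA and neutralising antibodies, "which have the potential to modulate PK or PD, or to produce adverse reactions". ADA incidence is one of the two primary endpoints.

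**The concern.** The AE table is the only visible planned display that links antibody status to adverse events. Its grouping variable is fixed by what happens at any time after baseline, while the AEs it counts run from the first dose. A participant who is negative at baseline, reacts on the Week 0 dosing day and first tests positive at Week 40 appears as an AE in an ADA-positive participant.

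AEs from the period before detection are thus mixed with AEs from the period after it. If ADA does raise the rate of some reaction, the mixing pulls the ADA-positive rate back towards the ADA-negative rate. In a safety study that is the unwelcome direction of error, because a table showing little difference could be read as evidence that antibodies are harmless.

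**Working it through.** **Inputs.** From the documents: scheduled post-baseline samples at Weeks 12, 26, 40 and 52; on-treatment AEs counted up to 182 days after the last dose (SAP 6.2.2.3), which is Week 52 for two doses on schedule; and one earlier ADA rate, 9 participants or 25% (9/36) in the first-time-in-humans study (protocol 2.3.1). The plan attaches no figure to this table, so there is none to reproduce. AE rates, ADA rates and sampling fractions below are assumptions, shown as ranges.

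**1. Share of AEs before first detection.** At a constant AE rate, the share is w/52 for a first positive at Week w:

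| First positive | Share of 52-week AEs before it |
|---|---|
| Week 12 | 12/52 = 23% |
| Week 26 | 26/52 = 50% |
| Week 40 | 40/52 = 77% |
| Week 52 | 52/52 = 100% |

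If the four weeks are equally likely, the mean is (12 + 26 + 40 + 52)/(4 × 52) = 62.5%.

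**2. Effect when ADA has no effect.** If AEs are independent of ADA and everyone is followed for 52 weeks, ever-positive and never-positive participants have the same expected AE count. A simulation with 25% ever-positive and 1.2 AEs per participant gave a rate ratio of 1.00. If 5–15% stop at Week 26 with two samples, the risk ratio is 1.01–1.04.

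**3. Effect when ADA has an effect.** Let the true rate ratio after detection be R, with persistent ADA and t = w/52. The ratio shown by the table is the mean of t + R(1 − t), which is 0.625 + 0.375R:

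- R = 2: 0.625 + 0.750 = 1.375, about 1.38
- R = 3: 0.625 + 1.125 = 1.75
- R = 5: 0.625 + 1.875 = 2.50

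**4. Unscheduled samples, if they were counted.** Assume no true relation. Let P be the chance of being ever positive over four scheduled samples, treated as independent, so the chance per sample is p = 1 − (1 − P)^(1/4). One extra sample gives P5 = 1 − (1 − p)^5. If a fraction f of participants with the event have the extra sample, their chance of being positive is P′ = P + f(P5 − P). With event risk q, the risk ratio, positive versus negative, is

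[qP′/(qP′ + (1 − q)P)] ÷ [q(1 − P′)/(q(1 − P′) + (1 − q)(1 − P))].

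Example with P = 25%, q = 2%, f = 1: p = 0.0694 and P5 = 0.302. The two risks are 0.0241 and 0.0186, a ratio of 1.29. Over P = 5–25%:

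| Event | f | Null risk ratio |
|---|---|---|
| Any AE (q = 70%) | 2–10% | 1.00–1.01 |
| Any AE (q = 70%) | 100% | 1.07–1.08 |
| Rare triggered event (q = 2%) | 50–100% | 1.13–1.29 |

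These are near upper limits. With durable ADA, a later scheduled sample would usually be positive anyway.

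**The case against.** A reader might infer that samples drawn because of an AE are counted, and that the extra testing builds in an association between ADA and AEs. The documents do not support this. The SAP neither includes nor excludes unscheduled samples. The protocol 7.5 sampling is optional and limited to potential type III events. For all AEs the effect under step 4 is about 1% at most when up to 10% of participants with an AE have an extra sample. What stands is an unspecified rule that could matter for the immune-complex AESI alone.

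A reader might also infer that AEs before the first positive sample cannot be due to antibody. That does not follow. Scheduled samples are up to 14 weeks apart (Week 12 to 26, Week 26 to 40), so antibody can precede detection by about that long. Participants given active drug in the parent studies enter after about a year of exposure and may already be positive at baseline. The timing argument therefore concerns detection, and any split has to deal with baseline positives. This objection stands and shapes the fix.

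Finally, the study has no hypotheses, the table is descriptive, and the SAP does not say that it will support a causal statement. AESI profile tables already report time to onset, and ADA results are shown by visit. Those points limit the consequence. They do not remove it, because no visible display puts AE onset and ADA timing together. The Output and Programming Specification was not available, and the text after the SAP 4.6 note and part of protocol 8.8 is redacted, so a rule may exist there.

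**Conclusion.** The point holds as a limit of the planned table. Ever-positive status, with no rule on AE onset, counts AEs before detection as AEs in ADA-positive participants and weakens any real association: a true rate ratio of 2 would show as about 1.38, and 5 as 2.50. Those figures assume a constant AE rate, persistent ADA, complete follow-up and equally likely first-positive weeks. Later detection would weaken it more, earlier detection less. The table does not manufacture an association; its main risk is false reassurance. The silence on unscheduled samples is a secondary gap, negligible for all AEs and relevant only to suspected type III events. This is a cheap improvement to the analysis and does not undermine the primary incidence summaries.

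**What to change.** In SAP 4.6:

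1. Keep the ever-positive column.
2. For the ADA-positive group, add a split of AEs, and of the hypersensitivity, immune-complex and injection-site AESIs, by onset before versus on or after the first confirmed-positive sample.
3. Let the Visit 1 sample count as a possible first positive, and show baseline-positive participants separately.
4. Give exposure-adjusted rates with the person-time for each period, since the two periods differ in length between participants.
5. Base ADA status on scheduled samples, and list separately any participant positive only on an unscheduled sample.
6. Label the split as relative to first detection, not to antibody onset.

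The cost is SAP wording and one more table split. Sample dates and AE start dates are already collected, so no new procedure is needed. AEs with partial start dates need a stated rule, for which the imputation convention in SAP 6.2.6 could be reused. The remaining weakness is that antibody may arise up to about 14 weeks before the first positive sample, so some AEs placed before detection will have occurred with antibody present. That is why the split belongs beside the present column and should not replace it.
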